8.1.2 Secondary Objectives

- 2.a.To compare the diagnostic accuracy of FLT PET/CT with that of FDG PET/CT as an indicator of tumor response to therapy
- 2.b. To evaluate whether FLT tumor uptake prior to therapy or following completion of therapy are independent predictors of complete response to therapy
- 2.c. To evaluate whether there is a significant difference in tumor, selected normal organs ,and mediastinal blood pool FLT dynamic influx parameter (Ki),SUV at 1 hours and 2 hours post injection

- 2.d To estimate the diagnostic accuracy of percent change in SUV between pre-treatment and mid-treatment FLT PET/CT with regard to complete response to therapy

8.1.3 Analysis Plan

For the primary analyses, sensitivity and specificity will be estimated and 95% confidence intervals provided. Subjects with an FLT SUV greater than mediastinal blood pool activity will be considered FLT positive. In the early response arm, subjects with complete response (CR or Cr_u, **Table 6**) as determined by the CHESON revised response criteria will be considered disease negative (all others will be considered disease positive). In the residual mass arm, subjects with any malignant cells on biopsy will be considered disease positive.

For secondary objectives 2a and 2d, empirical ROC curves will be estimated, along with non-parametric AUCs and corresponding 95% confidence intervals. For 2b, we will evaluate the ability of FLT to predict clinical response independent of other known predictors using logistic regression. For aim 2c, we will test for differences using signed-rank tests.

No stratification based on lymphoma histology or treatment is planned due to the small amount of expected variability in treatments available.

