Even though these initial studies appear promising, the evaluation of residual masses after standard chemotherapy in lymphomas continues to present as a clinical dilemma. We therefore intend to investigate the ability of [^{18}F]FLT PET to differentiate between residual viable tumor and non-viable masses after the conclusion of standard chemotherapy. In this protocol we will include individuals with FDG positive residual masses to determine if they represent active disease based on biopsy or clinical follow-up.

1.7 Findings as of March 1, 2013:

To date, we have 22/30 patients in the residual mass arm and 8/40 patients in the early response arm. After review of data we have noted that [^{18}F]-FLT PET/CT appears to better differentiate viable lymphomatous masses from benign inflammatory processes than [^{18}F]-FDG. This

suggests that in specific settings [^{18}F]-FLT may help [^{18}F]-FDG in predicting response to therapy.

2 Rationale

FDG PET/CT has emerged as a powerful functional imaging tool for staging, restaging, and response assessment of lymphomas. In 2007, the American Society of Clinical Oncology, released new guidelines incorporating FDG PET in the evaluation of treatment response in non-Hodgkin's and Hodgkin's lymphoma.(21) It is well known that FDG PET/CT imaging improves differentiation between viable and non-viable residual masses; however FDG accumulates in inflammatory lesions also, limiting its specificity. FLT PET/CT, with uptake correlation with cellular proliferation, may serve as a more accurate predictor of early (intra therapy) therapy response and be more accurate than FDG PET/CT in differentiating between residual tumor and non-viable mass post therapy.

3 Imaging Agent Information

3'-deoxy-3'- ^{18}F fluorothymidine (FLT)

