5.1.2 For subjects enrolling in the residual mass arm

Patients enrolled in an NIH Clinical Center lymphoma therapy protocol having a residual mass ≥ 1 cm in longest dimension as measured by the CT component of the PET/CT with FDG uptake greater than that of mediastinal blood pool will undergo an FLT PET/CT within 2 weeks of the post treatment FDG PET/CT study. Patients on other lymphoma therapies from outside institutions, must have a FDG PET/CT positive mass ≥ 1 cm, with uptake greater than that of mediastinal blood pool (81). Participant will undergo a repeat FDG PET/CT scan if the original FDG/PET imaging performed at an outside institution is not of "adequate imaging quality" for subjects enrolling in the residual FDG mass. The patient will undergo an FLT PET/CT within 2

weeks of the FDG PET/CT. Patients will undergo clinically indicated biopsy of the residual mass after FLT PET/CT imaging. Fine needle aspiration (FNA) will be performed when biopsy is not possible. If a biopsy is not medically indicated, then the patient will be followed medically by the Lymphoma Team or by their outside oncologist.

The FLT SUV will be compared with pathological response, with the presence of any viable lymphoma cells on biopsy being considered positive for malignancy. For patients who do not undergo biopsy, the absence of tumor will be assessed by lack of lesion progression on routine medical follow-up. An FLT SUV greater than mediastinal background will be considered positive for malignancy.

5.2 [¹⁸F]FLT PET/CT imaging

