5.3 Pathology (residual mass arm only)

In patients with FDG avid residual masses (uptake greater than mediastinal blood pool) who would routinely undergo biopsy or fine needle aspiration (FNA), the pathology results will be collected and compared with the corresponding FLT SUV. The presence of any viable lymphoma cells will be considered positive for residual malignancy. Biopsy is not medically

indicated in many patients undergoing therapy and therefore, determination of active disease will be based on clinical follow-up in those patients.

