7.2.2 Residual Mass arm

The presence of viable lymphoma cells on biopsy/FNA or absence of lesion progression on medical follow-up will be considered positive for residual malignancy.

8 Statistical Section

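### Section 8.1.3 scores a residual mass as diseased on any malignant cells at biopsy, while 5.1.2, 5.3 and 7.2.2 ask for viable lymphoma cells and FNA is a planned tissue source: the primary reference standard needs one definition

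*Combined protocol and SAP*

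**What the plan says.** The second primary objective (8.1.1, item 1.b) is the diagnostic accuracy of FLT PET/CT in residual masses. The reference standard for it appears in four places.

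- Section 8.1.3, which governs the primary estimate: "In the residual mass arm, subjects with any malignant cells on biopsy will be considered disease positive". It mentions neither viability, nor FNA, nor patients without tissue.
- Section 5.1.2 compares FLT SUV with pathology, "with the presence of any viable lymphoma cells on biopsy being considered positive for malignancy". It provides for FNA where biopsy cannot be done. For patients who are not biopsied, "the absence of tumor will be assessed by lack of lesion progression on routine medical follow-up".
- Section 5.3, which covers biopsy and FNA: "The presence of any viable lymphoma cells will be considered positive for residual malignancy". It adds that many patients have no medical indication for biopsy, and that "determination of active disease will be based on clinical follow-up in those patients".
- Section 7.2.2: "The presence of viable lymphoma cells on biopsy/FNA or absence of lesion progression on medical follow-up will be considered positive for residual malignancy".

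Section 1.6 states the question for this arm: whether FLT can "differentiate between residual viable tumor and non-viable masses after the conclusion of standard chemotherapy".

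**The concern.** The target condition is viable lymphoma, but the sentence that defines disease for the analysis carries neither qualifier. A treated mass with recognisable but non-viable tumour would be disease positive under the literal words of 8.1.3 and disease negative under the tissue criterion elsewhere. Such a mass is not remote from the protocol's own thinking: section 1.3 describes the imaging task as telling viable tumour from necrosis or fibrosis, and section 1.5 ties FLT uptake to proliferation.

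The word biopsy raises a second problem. A patient whose only tissue is an FNA showing viable lymphoma is positive under 5.3 and 7.2.2, but 8.1.3 taken literally has no rule that makes that patient positive.

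Section 8.1.4 expects about 15 diseased and 15 non-diseased patients and justifies the size by lower confidence bounds above 50%. With groups this small, moving two or three patients between columns is enough to matter.

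**Working it through.** **The plan's own figures.** Inputs from 8.1.4: 30 patients and 50% with positive pathology, so 30 × 0.50 = 15 positives and 15 negatives. The exact (Clopper-Pearson) 95% lower bound for x out of n is the 0.025 quantile of a Beta(x, n − x + 1) distribution. For n = 15:

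| x/n | Calculated | Table 8 |
|---|---|---|
| 12/15 | 0.519 | 0.52 |
| 13/15 | 0.595 | 0.60 |
| 14/15 | 0.681 | 0.68 |

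Table 8 reproduces. It depends only on n = 15, so neither definition changes it.

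**Tissue wording side by side.**

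| Section | Cells required | Tissue source | No tissue |
|---|---|---|---|
| 8.1.3 | any malignant | biopsy | no rule |
| 5.1.2 | viable lymphoma | biopsy; FNA if biopsy not possible | no progression means no tumour |
| 5.3 | viable lymphoma | biopsy or FNA | clinical follow-up |
| 7.2.2 | viable lymphoma | biopsy or FNA | no progression means malignancy |

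The sections other than 8.1.3 agree on the cells. On follow-up, 5.1.2 and 7.2.2 give opposite answers.

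**What reclassification could do.** The number of masses with only non-viable tumour is not in the documents, so k below is an assumption. Start from 13/15 sensitivity and 14/15 specificity, the counts in Table 8 nearest to the anticipated 85% and 90%.

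If k such masses are FLT negative, each moves from true negative to false negative. Sensitivity becomes 13/(15 + k) and specificity (14 − k)/(15 − k):

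| k | Sensitivity | Lower bound | Specificity |
|---|---|---|---|
| 0 | 13/15 = 0.867 | 0.595 | 14/15 = 0.933 |
| 1 | 13/16 = 0.812 | 0.544 | 13/14 = 0.929 |
| 2 | 13/17 = 0.765 | 0.501 | 12/13 = 0.923 |
| 3 | 13/18 = 0.722 | 0.465 | 11/12 = 0.917 |

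If instead one such mass is FLT positive, it moves from false positive to true positive. Sensitivity becomes (13 + 1)/(15 + 1) = 14/16 = 0.875, lower bound 0.617, and specificity becomes 14/(15 − 1) = 14/14. Both estimates rise.

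**FNA.** Suppose one of the 13 true positives was proven by FNA alone. Without that patient among the positives, sensitivity is (13 − 1)/(15 − 1) = 12/14 = 0.857, lower bound 0.572. Specificity is then 14/16 = 0.875 if the patient is scored disease negative, or still 14/15 if left out. The plan does not say which. One patient is again an assumption.

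**The case against.** The best defence is that 8.1.3 is a loose paraphrase. The protocol states the viable-cell criterion three times, once in a section devoted to pathology, and nothing tells a pathologist or analyst to count dead cells as malignant. Read as a whole, the document probably intends one rule. That stands as a judgement about intent, and it limits the likely harm. It does not remove the conflict, because 8.1.3 is the text from which the primary estimate would be calculated.

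A reader might infer that every mass with only dead tumour turns a correct negative scan into a false negative, so that sensitivity is biased downward. The documents do not support this. Entry to the arm requires FDG uptake above mediastinal blood pool (4.1.1), and the Precis calls FLT uptake in inflammation less prominent than FDG uptake, not absent. Some masses of this kind could be FLT positive, and those would raise sensitivity.

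A reader might also take three patients out of 30 as a plausible share. No frequency is given. Section 5.3 says many patients are not biopsied, so the tissue rule applies to fewer than 30.

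Finally, the difference between malignant and lymphoma might suggest a need to handle other cancers separately. Documented lymphoma is an entry requirement and no section anticipates other tumours, so that would be a preference and is not part of this point.

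**Conclusion.** The inconsistency is real and lies in the reference standard of a primary objective. Section 8.1.3 departs from the tissue criterion in 5.1.2, 5.3 and 7.2.2 and from the aim in 1.6, and it has no rule for disease proven by FNA.

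The size of any effect cannot be determined from the documents. It is nil if no mass holds only non-viable tumour, or if 8.1.3 is applied as the other sections intend, and if no patient's disease rests on FNA alone. Under the assumed counts, two reclassified FLT-negative masses bring the sensitivity bound to about 0.50 and three bring it below, while specificity barely moves. An FLT-positive mass acts the other way. A statement that the plan biases sensitivity in a known direction would therefore go too far. The sample-size calculation is sound on its own terms and does not need to change.

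The neighbouring gap belongs to the same correction: for patients without tissue, 7.2.2 and 5.1.2 classify absence of progression in opposite ways, and 8.1.3 does not address these patients. Correcting the cell criterion alone would still leave the primary analysis without a complete definition of disease.

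**What to change.** In 8.1.3, define disease positive in the residual mass arm as any viable lymphoma cells on biopsy or FNA, and state that non-viable tumour alone is disease negative. In the same edit, reconcile 7.2.2 with 5.1.2 on what absence of progression means for patients without tissue, and carry the reconciled rule into 8.1.3, so that all four sections share one definition covering biopsy, FNA and follow-up.

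This should be settled before the final analysis: section 1.7 reports 22 of 30 patients already enrolled in this arm and data already reviewed. The cost is a sentence or two in 8.1.3 and a wording correction where 7.2.2 and 5.1.2 disagree. It uses pathology and follow-up data already planned, with no new procedures or patients and no change to Table 8.

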8.1.4 Sample size

We plan to enroll 40 participants in the first arm and 30 participants in the residual tumor arm.

In the first arm, we assume that patients enrolled in this trial come from a randomized trial of DA-EPOCH-R vs. R-CHOP. With DA-EPOCH-R treatment, the expected response rate is 74%(92), while with R-CHOP it is 50%. (21). If we assume half of the patients enrolled in this trial will receive DA-EPOCH-R and the other half will receive R-CHOP, the average response rate is 62%, which will provide about 25 responders, who will contribute to estimates of sensitivity. About 15 patients will be non-responders and will contribute to estimates of specificity. The lower bounds for sensitivity are given in **Table 7**. Lower bounds for specificity are given in **Table 8**.

For the second primary objective, we assume that the 50% of patients with FDG positive residual disease will have positive pathology.(93) This provides 15 positives and 15 negatives. **Table 8** provides lower bounds for confidence intervals for sensitivity and specificity for this objective.

The following table provides expected lower bounds for 95% confidence intervals given observed values of sensitivity and specificity for a sample size of 15. We anticipate sensitivity and specificity to be about 85% and 90%, respectively. Hence, the sample size will provide lower bounds above the chance threshold of 50%.

Table 7

Sensitivity (n=25)	Expected lower bound of exact 95% CI
20/25(=.80)	0.59
21/25(=.84)	0.64
22/25(=.88)	0.69

Table 8

Sensitivity/Specificity (n=15)	Expected lower bound of exact 95% CI
12/15 (=0.8)	0.52
13/15 (=0.87)	0.60
14/15 (=0.93)	0.68

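### The primary analysis rule for the residual mass arm omits patients without biopsy, and the sections that do cover them contradict each other

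*Combined protocol and SAP*

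**What the plan says.** Section 8.1.3 sets the reference standard for the sensitivity and specificity estimates. For the early response arm the rule is complete: complete responders are disease negative and "all others will be considered disease positive". For the residual mass arm there is one sentence: "In the residual mass arm, subjects with any malignant cells on biopsy will be considered disease positive". It does not mention FNA, disease-negative status or patients without tissue.

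Other sections expect such patients and say how to judge them:

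- Section 1.6 says residual masses are studied "to determine if they represent active disease based on biopsy or clinical follow-up".
- Section 5.1.2 allows FNA where biopsy cannot be done, and adds: "If a biopsy is not medically indicated, then the patient will be followed medically by the Lymphoma Team or by their outside oncologist". It then says: "For patients who do not undergo biopsy, the absence of tumor will be assessed by lack of lesion progression on routine medical follow-up".
- Section 5.3 says of patients in whom biopsy is not indicated: "determination of active disease will be based on clinical follow-up in those patients".
- Section 7.2.2, the response criterion for this arm, says: "The presence of viable lymphoma cells on biopsy/FNA or absence of lesion progression on medical follow-up will be considered positive for residual malignancy".

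For sample size, Section 8.1.4 says "we assume that the 50% of patients with FDG positive residual disease will have positive pathology". From this it takes 15 positives and 15 negatives out of 30, and Table 8 gives the exact 95% lower bounds for groups of 15.

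**The concern.** The reference standard decides who enters the sensitivity denominator and who enters the specificity denominator. For an unbiopsied mass the document offers three texts that do not agree. Under 5.1.2, no progression means no tumor. Under 7.2.2, no progression means residual malignancy. Section 8.1.3 is silent.

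An analyst working from 8.1.3 alone could go two ways with an unbiopsied patient whose mass progresses. One is to count the patient as not positive, so that a correct FLT-positive reading becomes a false positive and specificity falls with no change in the test. The other is to leave the patient out, so that the estimate rests on a smaller group selected by the clinical decision to biopsy. Taking 7.2.2 literally would instead place non-progressing masses among the diseased and distort sensitivity.

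The choice should be fixed before analysis. Section 1.7 reports 22 of 30 patients already in this arm and a favourable impression of FLT from data review, so an open rule could be settled after the scan results are known.

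**Working it through.** **Inputs from 8.1.4.** N = 30; prevalence 50%; sensitivity about 85%; specificity about 90%; target, a lower bound above 0.50. The biopsied share is not in the documents, so it is an assumption and is shown as a range.

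**Plan's own figures.** 30 × 0.50 = 15 per group. Two-sided 95% Clopper-Pearson lower bounds are 0.519 at 12/15, 0.595 at 13/15 and 0.681 at 14/15. Table 8 gives 0.52, 0.60 and 0.68, so it reproduces.

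**Reading A: unbiopsied patients scored negative.** Let u be the share of diseased patients without biopsy. The negative group becomes 15 + 15u. The expected number of FLT-negative patients in it is 15 × 0.90 + 15u × (1 − 0.85), so

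expected specificity = (13.5 + 2.25u) / (15 + 15u).

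- u = 0.2: 13.95/18 = 0.775
- u = 0.3: 14.175/19.5 = 0.727
- u = 0.5: 14.625/22.5 = 0.650

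Expected sensitivity stays at 0.85 if biopsied diseased patients are typical, but on 15(1 − u) = 12, 10.5 or 7.5 positives.

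**Reading B: unbiopsied patients dropped.** Assume the same biopsied share in diseased and non-diseased patients. Counts are rounded to whole patients and the accuracies to the nearest attainable fraction.

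| Biopsied | Positive / negative | Sensitivity, lower bound | Specificity, lower bound |
|---|---|---|---|
| 80% (24) | 12 / 12 | 10/12, 0.516 | 11/12, 0.615 |
| 70% (21) | 11 / 10 | 9/11, 0.482 | 9/10, 0.555 |
| 60% (18) | 9 / 9 | 8/9, 0.518 | 8/9, 0.518 |
| 50% (15) | 8 / 7 | 7/8, 0.473 | 6/7, 0.421 |

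The dip at 70% is a rounding effect: 9/11 is 0.82, against 0.89 for 8/9. At 60% and 80% the bounds are about 0.52 or higher. At 50% both fall below 0.50. With 6 to 8 patients in a group, only 100% observed accuracy puts the bound above 0.50; with 5 or fewer, nothing does.

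**Reading C: follow-up standard of 5.1.2 and 5.3 applied.** Progression counts as positive and no progression as negative when there is no tissue. All 30 are classified. At 50% prevalence the split is 15/15 and Table 8 stands: 0.595 at 13/15 for sensitivity and 0.681 at 14/15 for specificity.

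**The case against.** Protocol and SAP are one document, and three of its sections supply a follow-up standard. Read as a whole, Reading C is the likeliest intention, and under it the stated precision survives at 50% prevalence. The Precis describes FLT imaging before standard-of-care biopsy, and FNA is a fallback, so the unbiopsied share may be small. The remark in 5.3 that biopsy is not indicated in many patients refers to patients undergoing therapy; 5.1.2 puts no number or adjective on it.

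Most of this stands, and it limits the point. A reader might infer that the plan recognises disease on biopsy alone, that an unbiopsied progressing mass is disease negative, and that the 15/15 precision therefore fails. The documents do not support that. Section 8.1.3 has no exclusive wording and no complement, 5.3 ties active disease to follow-up where there is no biopsy, Table 8 is arithmetically right, and no biopsy fraction is given from which to derive a shortfall.

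The objection does not remove the gap. Section 8.1.3 governs the primary estimate and does not refer to the follow-up standard. Section 7.2.2 contradicts 5.1.2 on what absence of progression means. That progression counts as positive is implied by 5.1.2 and 5.3 but not written. No follow-up period is stated for this arm.

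**Conclusion.** The omission and the contradiction are real and concern the reference standard of a primary objective. Section 8.1.3 leaves unbiopsied patients unaddressed, and 5.1.2, 5.3, 7.2.2 and 8.1.3 do not yield one rule. The 15/15 split and Table 8 are conditional on every patient being classifiable; they are not shown to be wrong.

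The size is illustrative. It rests on the plan's 50%, 85% and 90% and on an assumed unbiopsied share. Scoring unbiopsied patients negative would lower expected specificity from 0.90 to between 0.775 and 0.65 for u from 0.2 to 0.5. Dropping them leaves bounds near the 0.50 target at 60% to 80% biopsied and below it at 50%. Because biopsy is done on clinical indication, the share could differ between diseased and non-diseased patients. Reading B would then carry selection bias as well as lost precision, and the documents give no basis for quantifying it.

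**What to change.** Reconcile 5.1.2, 5.3, 7.2.2 and 8.1.3 into one composite reference standard, set out in full in 8.1.3:

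- Tissue obtained, by biopsy or FNA: status follows the tissue result.
- No tissue: progression on follow-up is disease positive and no progression is disease negative, over a stated follow-up period and with progression defined.

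Correct 7.2.2 to match. Keep all 30 patients in the primary estimate, and report sensitivity and specificity in the biopsy- or FNA-verified subset as a sensitivity analysis. In 8.1.4, restate the 50% assumption as the proportion positive by the composite reference instead of by pathology, and note the wider bounds for the verified subset. Fix the rule before FLT results are compared with disease status.

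The cost is wording in a few sections and one extra table, whose subset bounds will look less favourable than Table 8. Section 6.6 already allows follow-up clinical data from referring physicians after a patient leaves the study, so the rule uses a data source the protocol permits.

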1.1.2 Secondary Objectives

- To compare the diagnostic accuracy of FLT PET/CT with that of FDG PET/CT as indicators of tumor response to therapy
- To evaluate whether FLT tumor uptake either prior to therapy and/or following completion of therapy are independent predictors of complete response to therapy
- To evaluate whether there is a significant difference in tumor, selected normal organs, and mediastinal blood pool FLT dynamic influx parameter (Ki), SUV at 1 hours and 2 hours post injection
- To estimate the diagnostic accuracy of percent change in SUV between pre-treatment and mid-treatment FLT PET/CT as an indicator of complete response to therapy

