4.1 Eligibility Criteria

4.1.1 Inclusion Criteria

- Participant must be enrolled in a lymphoma therapy study at the NIH Clinical Center OR be enrolled in the CALGB 50303 study at another site OR undergoing a new course of treatment of lymphoma at another facility.
- Participants must have a clinical course consistent with lymphoma and have available documentation of lymphoma from either the NCI or from an outside pathology laboratory.
- Participant must be 18 years or older
- ECOG Performance score of 0 or 1
- Ability to provide informed consent. All patients must sign a document of informed consent indicating their understanding of the investigational nature and risks of the study before any protocol related studies are performed.

For subjects enrolling in early response arm

- Must be enrolled in CALGB 50303 or a lymphoma therapy study at the NIH Clinical Center or undergoing a new course of treatment of lymphoma at another facility

- Must not have begun lymphoma therapy for this tumor occurrence/ relapse
- Prior completed therapy does NOT affect eligibility

For subjects enrolling in the residual FDG avid mass arm

- Must have a residual FDG PET positive mass ≥ 1 cm, with uptake greater than that of mediastinal blood pool (81)
- Participant will undergo a repeat FDG PET/CT scan if the original FDG/PET imaging performed at an outside institution is not of adequate imaging quality for subjects enrolling in the residual FDG mass arm.

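### Objective 2a needs a named arm and a paired FLT-minus-FDG AUC difference; if it is applied to the residual-mass arm, entry on FDG uptake tilts the comparison toward FLT

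*Combined protocol and SAP*

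**What the plan says.** Section 8.1.2 states objective 2a as "To compare the diagnostic accuracy of FLT PET/CT with that of FDG PET/CT as an indicator of tumor response to therapy"; section 1.1.2 has nearly the same wording. Neither names an arm.

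The analysis in 8.1.3 covers 2a and 2d together: "empirical ROC curves will be estimated, along with non-parametric AUCs and corresponding 95% confidence intervals". Objective 2d is not a comparison, so this sentence describes estimation tracer by tracer. The only paired test in the plan belongs to another objective: "For aim 2c, we will test for differences using signed-rank tests".

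Both tracers are imaged in the same patients within set time windows (5.1.1, 5.1.2), and their SUVs are recorded side by side (Tables 3 and 4).

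For the residual-mass arm, section 4.1.1 sets the entry condition: "Must have a residual FDG PET positive mass ≥ 1 cm, with uptake greater than that of mediastinal blood pool". Section 5.1.2 repeats the FDG condition for NIH and outside patients. FLT positivity in 8.1.3 uses the same kind of threshold, mediastinal blood pool.

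Two places frame residual masses as a contest between tracers. The Rationale (section 2) says FLT may "be more accurate than FDG PET/CT in differentiating between residual tumor and non-viable mass post therapy". Section 1.7, written with 22 of 30 residual-mass patients and 8 of 40 early-response patients enrolled, reports that FLT "appears to better differentiate viable lymphomatous masses from benign inflammatory processes" than FDG does.

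**The concern.** There are two separate issues.

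**The comparison is not specified.** Two AUCs, each with its own interval, do not give an interval for their difference. The two estimates come from the same patients and are likely to be positively correlated. Treating them as independent, or looking for non-overlap of the intervals, then overstates the uncertainty. With 40 patients in one arm and 30 in the other, there is little precision to spare.

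**The comparator may be selected on.** If 2a is run in the residual-mass arm, every patient is there because FDG was positive. At the entry cut FDG cannot call anyone negative, and its ROC curve uses only the upper part of its range. FLT is affected only indirectly, through its correlation with FDG. Two tracers of equal accuracy would then look unequal, in FLT's favour on specificity and AUC. No section mentions this selection.

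**Working it through.** **The plan's own figures.** None is given for 2a. The class sizes in 8.1.4 reproduce: 0.5 × 0.74 + 0.5 × 0.50 = 0.62; 40 × 0.62 = 24.8 responders and 15.2 non-responders; 30 × 0.50 = 15 positive and 15 negative residual masses. Under 8.1.3, complete responders are disease-negative, so the early arm has about m = 15 disease-positive and n = 25 disease-negative patients.

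**Step 1: what pairing is worth.** Assumptions, not in the documents: AUC 0.90 (FLT) and 0.75 (FDG), and r, the correlation between the two AUC estimates (not between SUVs).

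Hanley-McNeil: SE² = [A(1−A) + (m−1)(P₁−A²) + (n−1)(P₂−A²)] / (mn), with P₁ = A/(2−A) and P₂ = 2A²/(1+A).

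- A = 0.90: P₁ = 0.8182, P₂ = 0.8526; (0.0900 + 14 × 0.0082 + 24 × 0.0426)/375 = 0.00327; SE = 0.057.
- A = 0.75: P₁ = 0.6000, P₂ = 0.6429; (0.1875 + 14 × 0.0375 + 24 × 0.0804)/375 = 0.00704; SE = 0.084.

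SE of the difference = √(0.057² + 0.084² − 2r × 0.057 × 0.084), computed with unrounded SEs:

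| r | SE of difference | 95% half-width (1.96 × SE) |
|---|---|---|
| 0 (pairing ignored) | 0.102 | 0.20 |
| 0.5 | 0.074 | 0.15 |
| 0.7 | 0.060 | 0.12 |

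A simulation of DeLong's paired method with the same AUCs and class sizes gave mean half-widths of about 0.19, 0.16 and 0.14 at marker correlations of 0, 0.3 and 0.6. Even paired, 2a is an estimation exercise.

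**Step 2: FDG at the entry cut in the residual-mass arm.** With 15 positive and 15 negative masses, all FDG-positive by entry, FDG sensitivity is 15/15 = 100% and specificity 0/15 = 0%. FLT cannot lose on specificity and cannot win on sensitivity. Six FLT-negative patients among the 15 tumor-free would already give an exact McNemar p of 2 × 0.5⁶ = 0.031.

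**Step 3: the continuous SUV.** Assumed binormal model: both tracers have a true AUC of 0.85, with tumor-free values N(0,1) and tumor values N(1.466,1), since √2 × Φ⁻¹(0.85) = 1.466. Patients enter only if FDG exceeds the cut. ρ is the FLT-FDG correlation within disease class.

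| Entry cut | Tumor-free kept | FDG AUC after entry | FLT minus FDG, ρ = 0 | ρ = 0.5 | ρ = 0.8 |
|---|---|---|---|---|---|
| 0 | 50% | 0.78 | 0.07 | 0.03 | 0.01 |
| 1.0 | 16% | 0.71 | 0.14 | 0.06 | 0.02 |

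The true difference is zero in every cell. FDG's AUC falls by 0.07 to 0.14 whatever ρ is. The false gap shrinks as ρ rises, because selecting on FDG also lowers FLT's AUC.

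**Step 4: a version tied to the documents.** Section 1.3 quotes pooled FDG sensitivity of 84% and specificity of 90% in Hodgkin's lymphoma after first-line therapy. In the same type of model this implies an AUC of 0.946 before selection. Among FDG-positives, FDG's AUC is 0.82 and that of an equally accurate FLT is 0.95, 0.91, 0.87 and 0.84 at ρ = 0, 0.3, 0.6 and 0.8. The spurious advantage is 0.02 to 0.13.

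**The case against.** **2a may concern the early-response arm only.** Its wording is about tumor response, whereas primary objective 1b speaks of residual masses. This stands as an ambiguity. The Rationale is hedged and section 1.7 is an observation, not a planned analysis, so a reader who infers that 2a definitely covers the residual-mass arm goes further than the documents do. Nothing confines 2a to one arm either, so the part about selection must be conditional.

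**The full fall in FDG's AUC is not the false FLT advantage.** It is tempting to read 0.07 to 0.14 that way. Step 3 shows this is so only if the tracers are uncorrelated, and the gain from pairing itself presupposes correlation. Only the range down to about 0.01 is supportable.

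**No binary FLT-versus-FDG comparison is planned.** True; the 0% specificity is a consequence of entry, not a result the plan would tabulate. It still shows what any binary comparison there would mean. A repeat FDG scan, made when outside imaging is inadequate, could fall below the cut; this is a small exception.

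**The early-response arm is not neutral ground.** This stands. Table 6 defines complete response in FDG-avid disease partly by a negative PET, so FDG contributes to the truth label and the comparison leans toward FDG. Moving 2a there is better only if this is stated.

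**Much of the residual-mass reporting is already planned.** Primary objective 1b estimates FLT sensitivity and specificity in FDG-positive patients. What is missing is the limit on comparative claims.

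**2a is an unpowered secondary objective.** Agreed; the case rests on interval width and bias, not on power.

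**Conclusion.** The point holds in two parts of different strength.

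Unconditionally, 2a is a comparison for which 8.1.3 supplies neither an estimate of the difference, nor a method that uses the pairing, nor an arm. Under the assumptions in Step 1, ignoring the pairing inflates the standard error of the difference from 0.060–0.074 to 0.102. The documents give no AUCs or correlations for 2a, so the size is illustrative. The direction holds for any positive correlation.

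Conditionally on 2a being applied to the residual-mass arm, entry on FDG uptake fixes FDG at 100% sensitivity and 0% specificity at the entry cut, and tilts the AUC comparison toward FLT by about 0.01 to 0.14 under the assumed model with equal AUCs of 0.85. The 100% and 0% need no model; the AUC range does.

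A reader might infer that the observation in section 1.7 is itself an artefact of selection. The documents give no data by tracer and do not support that. Nor does selection favour FLT on every measure, since its sensitivity in that arm cannot exceed FDG's.

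This should be corrected, but it does not affect the primary analyses.

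**What to change.** In 8.1.3, separate 2a from 2d and add text to this effect:

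- Objective 2a is assessed in the early-response arm, at the mid-treatment scan, in patients with both scans.
- The estimate is AUC(FLT) − AUC(FDG), with a 95% confidence interval by the paired DeLong method or a patient-level bootstrap.
- Binary calls are compared by McNemar's test separately within disease-positive and disease-negative patients. The FDG cut must be written down: 8.1.3 defines positivity for FLT only, while 5.5.2 uses surrounding background for both tracers.
- The reference standard in this arm incorporates FDG PET status (Table 6), so the comparison leans toward FDG.
- In the residual-mass arm, FLT accuracy is reported as accuracy among FDG-positive masses: how many tumor-free masses FLT clears and how many tumors it misses. No claim that FLT is superior to FDG is made from that arm.

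The cost is a few lines of text and standard software, with no new patients, scans or procedures. The downside is narrower claims from both arms: a caveated comparison in one, and accuracy of FLT as an add-on to FDG in the other.
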